## 15.0 Statistical Considerations

*15.1 Data Analysis Plan:*

Preliminary Analyses to Determine Covariates Needed for Primary Analyses. The purpose of collecting data on potential covariates is to identify variables that are correlated with both the independent variable (social buffering condition, sex, pubertal stage) and the primary outcome measures. Those covariates that are associated with the independent and outcome variables will be controlled for in the primary analyses. Those that are not will be used to describe the sample, but will not need to be included in the analyses to obtain unbiased estimates. For each potential covariate, we will conduct correlations or t-tests with pubertal stage, and t-tests, ANOVAs, or chi-square tests (as appropriate) with sex and condition. If data do not confirm to modeling assumptions, we will use nonparametric analogs instead.

Preliminary Analyses of Imaging Data to Yield Primary Outcome Measures: fMRI data will be analyzed in FSL software (version 5.0.10) to generate voxel-wise contrast maps. Mean signal values will be extracted from these maps in a priori regions of interest for every participant using the methods described below. These preliminary analyses are used to generate the fMRI outcome variables of interest. The values of these outcome variables for each participant will be used in the general statistical analyses described in the next section. In total, these preliminary analyses will yield 6 primary task-related outcome variables, and 6 primary connectivity-related outcome variables.

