### 15.3 Statistical Analysis of MRI and non-MRI Outcome Variables:

The following is a list of the analyses that we will perform on the outcome measures. They are classified as to whether they are the primary or mediational analyses. All statistical analyses will be performed in R.

The primary analyses will consist of a series of multiple regression models. For each dependent variable, variation in neural activity, cortisol response, and heart rate response, we will begin by testing the three-way interaction between social buffering condition, sex, and pubertal stage for all outcomes. If the three-way interaction is not significant, we will then examine all two-way interactions. If the two-way interactions are not significant, we will then examine main effects only models. If the three-way interaction is significant, we will not examine any other model. If condition is significant as an interaction or as a main effect, we will examine all pairwise comparisons using Tukey's Honestly Significant Difference test.

Multiplicity of testing. We will correct for multiple comparisons using the Benjamini-Hochberg (BH) correction. The BH method works by controlling the false discovery rate, and relative to the Bonferroni's correction is more powerful, while still adequately protecting against Type I error (Williams, Jones, & Tukey, 1999).

Mediational Analysis. When changes in activity of brain regions differ by condition or condition by pubertal status and we also see condition or condition by pubertal status differences for cortisol, or heart rate, then we will examine whether brain activity differences mediate the neuroendocrine or autonomic differences. This will be examined using path analysis, while controlling for covariates identified in the preliminary

covariate analysis, and will be estimated using the lavaan package in R (Rosseel, 2012).

The significance of all indirect effects will be assessed using bias-corrected 95% confidence intervals (Efron & Tibshirani, 1986), where confidence intervals that are non-overlapping with zero will be considered significant.

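### The mediation model for Hypothesis 2 inherits a covariate screen that can drop measured common causes of brain response and physiology

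*Combined protocol and SAP*

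**What the plan says.** Section 15.1 describes a preliminary screen meant to "identify variables that are correlated with both the independent variable (social buffering condition, sex, pubertal stage) and the primary outcome measures". The rule is then: "Those covariates that are associated with the independent and outcome variables will be controlled for in the primary analyses". Covariates that fail are used descriptively and, in the plan's words, "will not need to be included in the analyses to obtain unbiased estimates". The tests are named: "we will conduct correlations or t-tests with pubertal stage, and t-tests, ANOVAs, or chi-square tests (as appropriate) with sex and condition". No significance level is given for them.

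Section 15.3 starts the mediation analysis only when condition, or condition by pubertal status, shows differences both in brain activity and in cortisol or heart rate; "then we will examine whether brain activity differences mediate the neuroendocrine or autonomic differences". On covariates it says: "This will be examined using path analysis, while controlling for covariates identified in the preliminary" covariate analysis, that is, the list from Section 15.1. An indirect effect counts as significant when its bias-corrected 95% interval excludes zero.

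Section 5.2 adds three local rules. HBQ scales enter if they differ by condition, pubertal stage or sex. Relationship quality enters if the conditions differ. Medication classes enter with no imbalance test. The plan states no assumption about confounding between mediator and outcome and no sensitivity analysis for it.

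**The concern.** Condition is randomised; brain response is not. In the path model, the link from brain response to cortisol or heart rate is therefore observational, and its confounders are common causes of those two variables. Whether such a variable is also related to condition, sex or puberty is beside the point for that link.

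The screen nonetheless requires a relation to one of those three. Randomisation makes association with condition a matter of chance, so a trait or day-of-test state unrelated to sex and puberty is normally dropped, however strongly it drives both brain and physiology. The estimated brain-to-physiology path then absorbs the shared influence, and the indirect effect inherits the bias. A positive result for Hypothesis 2 could reflect, say, a temperamental difference measured at Visit 1 rather than neural mediation of buffering.

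**Working it through.** **The plan's own figures.** The mediation power paragraph in Section 15.3 reports no numeric power, so it offers nothing to reproduce. The only reproducible figures are the minimum detectable f² values in Section 15.2, for the three-way interaction: 0.056 at n = 200 and 0.070 at n = 160. With the noncentral F test, λ = f²(u + v + 1), u = 3 and v = n − u − 1, I obtain 0.0556 and 0.0699. They do not bear on this point.

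**Step 1: chance of surviving the screen.** Inputs: three families of test (pubertal stage, sex, condition; Section 15.1), each at an assumed .05. For a variable unrelated to all three, P(at least one significant) = 1 − 0.95³ = 0.143. It is dropped about 86% of the time. Simulated retention was 12-15% for r of 0.2 or more.

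**Step 2: the bias when it is dropped.** Let C be the dropped variable, correlated r within condition with both the brain measure M and the physiological outcome Y, all with unit within-condition variance. If the true path b from M to Y is zero, the within-condition covariance of M and Y is r × r, so the fitted b tends to r². With an effect a of 0.8 SD on M, the spurious indirect effect has size 0.8r²:

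- r = 0.2: b = 0.04, indirect 0.032
- r = 0.3: b = 0.09, indirect 0.072
- r = 0.4: b = 0.16, indirect 0.128
- r = 0.5: b = 0.25, indirect 0.200

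Simulated mean indirect effects without C were 0.035, 0.071, 0.130 and 0.199 in absolute size. With a standard error for b of roughly 1/√200 = 0.071, the spurious b lies about 0.6, 1.3, 2.3 and 3.5 standard errors from zero.

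**Step 3: false mediation under the whole procedure.** Inputs from the plan: three arms, n = 200 (160 after the imaging loss allowed for in Section 15.2), the screen, the requirement of condition differences on both M and Y, and the bias-corrected interval. Assumptions: equal allocation, 0.8 SD effect on M, 0.5 SD direct effect on Y, b = 0, the values of r, and C unrelated to sex and puberty. Paths were fitted by least squares adjusted for sex and puberty, with 400 bootstrap resamples and 500 trials per row. A separate simulation used a joint-significance test of a and b. Rates are among trials that proceed to mediation (about 85% at n = 200).

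| r | Screen, joint test | Screen, bootstrap | C always adjusted, bootstrap |
|---|---|---|---|
| 0 | not run | 7.8% | 7.3% |
| 0.2 | 8% | 13.6% | 8.2% |
| 0.3 | 22% | 23.3% | 7.7% |
| 0.4 | 53% | 59.0% | 7.5% |
| 0.5 | 82% | 84.1% | 7.5% |

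Always adjusting gave about 5-6% with the joint test. At n = 160 the bootstrap rates were 19.9% against 6.9% (r = 0.3) and 79.7% against 7.2% (r = 0.5). At n = 200 with a 0.5 SD effect on M they were 30.6% against 10.6% and 80.5% against 8.6%.

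Cross-check: the screened rate should be about 0.857 × (rate with C omitted) + 0.143 × (rate with C included). In a separate bootstrap run, r = 0.4 gives 0.857 × 66.9 + 0.143 × 7.3 = 58.4%, and r = 0.5 gives 0.857 × 96.6 + 0.143 × 5.8 = 83.6%. Both are close to the table.

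**Step 4: where the problem does not arise.** If C correlates 0.3 with puberty, it is kept 99% of the time and the false rate at r = 0.3 is 7.0%. If condition has no effect on physiology, the mediation analysis is seldom reached: over all trials, false mediation was 0.3% to 3.4% (n = 160 or 200, effects of C from 0.2 to 0.5, joint test).

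**The case against.** **The screen is headed as serving the primary analyses.** For those it is defensible: condition is randomised, and a confounder of sex or puberty must relate to sex or puberty. A reader might infer that the primary condition effects are biased too; the documents do not support that. The fault lies in Section 15.3 carrying the list over.

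**The brain measure could be read as an independent variable in the path model, so the screen would cover it.** The text closes this off: covariates must be "correlated with both the independent variable (social buffering condition, sex, pubertal stage) and the primary outcome measures". Brain activity is on the outcome side, and none of the independent-variable tests involves it.

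**The entry condition protects.** It does when condition leaves physiology unchanged. It does not when condition has real effects on both measures, since it does not ask whether one causes the other. A reader might take the upper figures in the table as the plan's overall false-positive rate. They are conditional on reaching the mediation analysis and on assumed effects.

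**Many confounders would survive.** This stands. A reader might infer that inhibition, internalizing, wake time or caffeine would certainly be discarded. That assumes they vary with neither sex nor puberty at ages 11 to 14, and the documents do not say so. The HBQ rule requires no link to the outcome, and medication classes enter regardless, although that rule sits under stress hormones.

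**The analysis is exploratory.** Section 15.3 uses that word in its mediation power paragraph and warns there that mediation may be concluded when absent. But it attributes this to low power, Section 2.3 makes mediation one of two hypotheses, and a significance rule is set.

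**Conclusion.** The point holds for the mediation analysis only. As written, the plan would usually omit from the path model a measured common cause of brain response and physiology that is unrelated to sex and puberty, and its statement about unbiased estimates is wrong for that model. The consequence is small at r = 0.2, material at 0.3 and severe from 0.4, given real condition effects on both brain and physiology. The documents give none of these effect sizes or correlations, no screening level and no allocation ratio, so all are assumptions. The simulations used a simple condition effect rather than condition by puberty, and least squares rather than lavaan.

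It should not be inferred that adjustment restores exactly 5%. The bias-corrected interval ran at about 7-8% in the main setting even with no confounder, and reached 10.6% in one adjusted setting. A smaller run (300 trials, n = 160) gave 9% and 12% after adjustment.

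This should be fixed, but it is not a fatal flaw, because the primary condition effects are unaffected.

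**What to change.** In Section 15.3, stop using the Section 15.1 screen for the path models. Name a short fixed set of variables measured before the stressor and enter it in both the mediator and the outcome equation. Candidates are selected Visit 1 HBQ scales (for example internalizing and behavioral inhibition), diary items confirmed as recorded before the MISTiC, sex, pubertal stage and the medication classes already specified in Section 5.2. In Section 15.1, limit the statement about unbiased estimates to the primary condition, sex and puberty models.

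The data are already collected, but the list needs choosing. Seven HBQ scales from two reporters plus five diary items make 7 × 2 + 5 = 19 terms before medication, sex and puberty, against the 12 covariates assumed in Section 15.2; the set should stay near 12. Diary timing needs checking, since Section 5.2 says only that the entries concern that day and places questionnaires both before and after the scan.

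The cost is some degrees of freedom in each equation. Only measured confounding is removed, so the plan should also commit to stating, with any conclusion on Hypothesis 2, that unmeasured confounding of brain response and physiology remains possible.

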### **Physiological Measures.**

**Stress Hormones:** We will assay saliva samples for stress sensitive hormones: cortisol and alpha-amylase. Saliva will be collected using SalivaBio Oral Swabs (SOS) or passive drool and stored frozen at -20°C until shipped for assay. All testing will be conducted in the late afternoon to control for circadian rhythm. Medications will be recorded from parent report and classes of drug codes will be used to group meds by presumed mechanisms of action and will be entered as covariates (Granger et al., 2009). Systemic glucocorticoid medications are an exclusion criterion. For each analyte, we will calculate area under the curve from intercept (AUCi) to provide a single measure for the main analysis.

**Pubertal Hormones - DHEA, Testosterone, Estradiol:** Sufficient saliva will be obtained at sampling to assay for these additional pubertal hormones. These assays will be performed if we obtain a sex by condition by pubertal development (3-way) interaction on key outcome measures. If so, these measures may provide insight into the mechanism of these interactions ([Butler et al., 1989](#); [Mehta, Mor, Yap, & Prasad, 2015](#)).

**Physiological Recording:** Participants will wear standard Siemens physiological recording equipment for the MRI environment (respiration belt, and pulse oximeter or EKG leads). Samples will be collected throughout the entire MRI scan. Response measures will be computed by regressing the stress condition values on comparison condition values and saving the residual as the response measure.

All questionnaires and surveys are included in the ETHOS portal. Contact information and child age will be obtained from an existing registry of families who have expressed interest in child development research (specifically, parent name(s), address, phone number, email address, child

**PROTOCOL TITLE:** An MRI Study of Stress and Social Support

**VERSION DATE:** v.5.5 2022.09.20

name, child sex, and child birthdate). All other data will be acquired directly from the participants, and information obtained from the participant registry will be verified verbally with the parent.

**5.3 Study Duration:** Participants will attend two sessions. Each session will last approximately 2 hours.

- All participants will be enrolled and assessed within a 30-month period.
- Primary data analysis endpoints will be available within 1 year of the end of data collection (i.e., 42 months from initial enrollment).

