Task-based analysis: Math under social evaluative stress In first level analyses (single subject, single-run), math performance will be modeled for each participant using a voxel-wise multiple regression analysis with a task predictor (math trials vs. blank trials), 24 regressors for head motion (Satterthwaite et al., 2013) and additional regressors to model censored data points (motion spikes). In subsequent analyses, we will explore the utility of including other time varying individual differences variables (e.g., heart rate, respiration) that are known to contribute to the BOLD signal. However, since these measures are expected to vary by stress condition, removing the effects of these physiological variables may unintentionally remove effects of interest. Particular care will be taken to reduce the confound of head motion by censoring (identifying as artifact) any data point with absolute motion greater than 2 mm (1 voxel) or a framewise displacement greater than 0.5 mm, as well as the immediately preceding and following data points. Data points with DVARS values exceeding the

individual's 75th percentile plus two times the interquartile range will also be censored. Participants with more than 25% of data points censored for artifact will be excluded from further analyses.

Second level analyses (single-subject, multiple runs) will test the within-subject contrast of math performed with judges (social evaluative stress) relative to math performed alone (without social evaluation) to identify brain regions differentially activated by social evaluative stress. Based on prior literature, we will examine activation in 5 *a priori* regions of interest, including "pain-related" brain regions (dorsal anterior cingulate [dACC], left and right anterior insula) and "safety-related" or regulatory brain regions (ventromedial prefrontal cortex [vmPFC], and left and right dorsolateral prefrontal cortex [dlPFC]). For each subject, the mean percent change in MR signal (averaged across voxels) between judged math and math alone will be extracted from each of these 6 regions. This analysis will generate the 6 task-related brain activation outcome variables (listed in section 4.3) for each participant.

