cortex (left and right vmPFC and dlPFC). To determine whether connectivity varies as a function of stress, we will compare connectivity during the speech preparation scan to connectivity during the baseline resting state scan. Preprocessing steps will include motion correction, unwarping, and eddy-current correction. An initial voxel-wise multiple regression analysis will be performed to remove effects of head motion (24 predictors), and estimates of CSF and white matter signals (2 predictors) from each subject's data. Initial analyses will not include a predictor for global signal given evidence that the inclusion of global signal may falsely introduce anticorrelations in the data (Murphy et al., 2009; Saad et al., 2012). However, in exploratory analyses, we will examine the degree to which the results change when global signal is included in the model.

First-level (single-subject, single run) connectivity analyses on the residualized data will include the time course for a seed region and predictors for censored data points. Two separate regression models will be run, one using the bilateral amygdala as the seed region, and the other seeding connectivity in the hypothalamus.

Second-level (single-subject, multiple-runs) analyses will test the within-subject contrast of connectivity during anticipatory stress (speech preparation) relative to baseline resting state for each seed-region. Masks of a priori target brain regions of interest will be applied to resultant contrast maps to extract stress-related connectivity in the bilateral vmPFC and left and right dlPFC for each individual. This analysis will generate the 6 connectivity-related brain outcome variables (2 seed regions x 3 target regions) for each participant. Because difference scores (speech preparation minus baseline) can mask the direction of connectivity effects (positive vs. negative correlations), follow-up simple-effects analyses will assess connectivity separately in the speech preparation and resting state periods, using the same a priori seed and target regions. These follow-up simple-effects analyses will allow us to interpret the directionality of connectivity effects.

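### The six task-related brain outcomes are not corrected for heart rate but are tested as mediators of heart rate, so task-locked contamination could pass for mediation

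*Combined protocol and SAP*

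**What the plan says.** Hypothesis 2 (section 2.3) is that neural activity mediates physiological buffering. Heart rate is one of the primary outcomes in section 3.1. It is recorded in the same session as the BOLD data (section 5.2, Physiological Recording): "Samples will be collected throughout the entire MRI scan".

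For the task analysis, section 15.1 specifies a first-level model "with a task predictor (math trials vs. blank trials), 24 regressors for head motion", plus regressors for censored points. Cardiac and respiratory terms are deferred: "In subsequent analyses, we will explore the utility of including other time varying individual differences variables", which the plan describes with the words "e.g., heart rate, respiration) that are known to contribute to the BOLD signal". The reason given is that "since these measures are expected to vary by stress condition, removing the effects of these physiological variables may unintentionally remove effects of interest". For each of six regions, "the mean percent change in MR signal (averaged across voxels) between judged math and math alone will be extracted".

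For connectivity, section 15.1 uses an initial regression to "remove effects of head motion (24 predictors), and estimates of CSF and white matter signals (2 predictors"). It has no cardiac or respiratory term either.

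Section 15.3 makes mediation conditional. If both brain activity and cortisol or heart rate differ by condition (or by condition and pubertal status), "then we will examine whether brain activity differences mediate the neuroendocrine or autonomic differences". The path model adjusts only for covariates found in the preliminary screen, and an indirect effect counts as significant when its bias-corrected 95% interval excludes zero. Nothing says whether the corrected or the uncorrected brain measure is used when heart rate is the outcome.

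**The concern.** The plan's reason for leaving physiology in the signal is sound for the effect of condition on brain activity, because correction might strip out part of what is being studied. That reason does not carry over to a model with heart rate as the outcome. There, a variable that the plan says contributes to the mediator is also the dependent variable, so part of the brain-to-heart-rate path may be measurement overlap.

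The entry condition is not a reliable safeguard. If a partner changes heart rate, and that change reaches the task contrast, the contamination itself produces a condition difference in BOLD. At stake is the reading of a positive heart-rate result under Hypothesis 2: brain activity carrying the effect, or heart rate showing up in the scanner signal. Cortisol does not overlap directly with BOLD in this way.

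**Working it through.** **The plan's own figures.** The plan states no error rate for the mediation test. The nearest figure is the minimum detectable f² in section 15.2, and it reproduces. With 11 design terms, 12 covariates and u = 2, v = 200 − 24 = 176, and noncentrality f²(u + v + 1) = 0.056 × 179 = 10.0 gives power 0.809. At n = 160, 0.070 × 139 = 9.7 gives power 0.795. The point below does not depend on these figures.

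**Step 1: which heart-rate changes reach the task outcome.** Assume an additive contribution within a run:

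BOLD(t) = baseline + β·task(t) + γ·HR(t) + noise, with HR(t) = c + h·task(t).

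The fitted task effect is β + γh, and the constant γc goes into the baseline. The extracted outcome, judged minus alone, is therefore (β_J − β_A) + γ(h_J − h_A). A sustained shift c drops out. Contamination needs a task-locked component h that differs between the two runs, and false mediation needs that difference to vary by arm and to track the heart-rate response measure.

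Simulation agrees (n = 200, parent effect 0.8 SD, no neural effect). With a sustained additive shift, the raw run-mean difference correlated 0.996 with heart rate, but the math-versus-blank contrast correlated 0.00 and its condition test was significant in 4.8% of trials. A further check of the sustained case gave 0% false mediation. Task-locked contamination of assumed strength 0.3 to 0.5 gave 25% to 51%.

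**Step 2: why both paths appear.** Let r be the within-arm correlation between heart rate and the BOLD contrast due to contamination, and d the parent effect on heart rate in SD units. Neither is in the documents; both are assumed. With no neural effect, the parent-versus-none shift in BOLD is r·d in SD units. With equal arms (assumed; 200/3 ≈ 67 each) its standard error is about √(2/66.7) = 0.173. The brain-to-heart-rate path has t ≈ r√196/√(1 − r²).

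| r | brain-to-heart-rate t | condition-to-brain z, d = 0.5 | condition-to-brain z, d = 0.8 |
|---|---|---|---|
| 0.1 | 1.41 | 0.29 | 0.46 |
| 0.2 | 2.86 | 0.58 | 0.92 |
| 0.3 | 4.40 | 0.87 | 1.39 |
| 0.4 | 6.11 | 1.15 | 1.85 |

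From r = 0.2 the brain-to-heart-rate path is readily significant, and the condition-to-brain path is what limits the error rate.

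**Step 3: simulated rates.** Three arms, n = 200, one region, condition acting on heart rate only, BOLD = [r/√(1 − r²)]·HR + noise. Entry condition: both three-arm ANOVAs at p < .05, before Benjamini-Hochberg. Mediation is declared when the 95% interval for the parent indirect effect excludes zero.

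| Interval | d | r = 0 | 0.1 | 0.2 | 0.3 | 0.4 |
|---|---|---|---|---|---|---|
| Bias-corrected bootstrap (400 trials) | 0.5 | 0% | 1.0% | 4.0% | 10.5% | – |
| Bias-corrected bootstrap (400 trials) | 0.8 | 0.5% | 1.2% | 10.5% | 21.5% | – |
| Monte Carlo, two runs | 0.5 | – | – | 3% | 7–9% | 11–15% |
| Monte Carlo, two runs | 0.8 | – | – | 7–8% | 20–21% | 36% |

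Simulation error is modest: at 21.5% with 400 trials the standard error is √(0.215 × 0.785/400) = 2.1 points. At n = 160, d = 0.8 and r = 0.3 the bootstrap rate is 16.2%.

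**Step 4: Benjamini-Hochberg.** The plan does not define the family. With 14 tests assumed (12 brain outcomes, heart rate, cortisol) and noise independent across regions, the per-region rates at r = 0.2, 0.3 and 0.4 fall to 1%, 3% and 6% (d = 0.5) and 3%, 9% and 22% (d = 0.8). If all six task regions are equally contaminated, which is a further assumption, the chance of at least one false mediation is 5%, 12% and 20% (d = 0.5) and 10%, 36% and 66% (d = 0.8).

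**The case against.** The strongest reply is that the task outcome is a within-run contrast. A reader might infer that any lowering of heart rate by a partner will move the brain mediators. The documents do not support this: under an additive contribution a sustained shift cancels, and no figure is given for task-locked heart-rate change or for how it differs by arm. The plan's statement that physiology varies concerns stress condition; it does not say that buffering arms differ. The objection stands and confines the point to task-locked contamination.

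A reader might also extend the point to the six connectivity outcomes. Removing CSF and white-matter signals is already a partial physiological correction, and the simulations model signal amplitude, not a correlation-based mediator. No rate can be given there.

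Third, the plan discloses the issue, intends to explore correction, and calls the mediation analysis exploratory when discussing its power. It also warns there that complete mediation might be concluded when mediation is only partial or non-existent. This is a fair mitigation, but that warning is about power, and the exploration is not tied to the heart-rate model.

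Finally, correction may remove true effects. This stands, and it is why the corrected version should not overrule the uncorrected one.

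**Conclusion.** The concern holds for the six task-related outcomes when heart rate is the mediation outcome. The plan names the contaminant, leaves it in the mediator, and has no rule for that model. Task-locked contamination that differs by arm can then meet the entry condition and give a significant indirect effect with no neural effect.

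The size is conditional. Over the assumed range, false mediation per region is about 1% (r = 0.1) to 36% (r = 0.4, d = 0.8) with three arms and before Benjamini-Hochberg, and lower per region after it. At r = 0.1 it is below 2%. The figures require a real condition effect on heart rate, an additive contribution, and r and d values that the documents do not supply.

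It would go too far to infer that Hypothesis 2 cannot be answered for heart rate, or that the uncorrected measure is wrong in general. Its use for the condition effects on brain activity is defensible. What is missing is a companion analysis that shows whether a heart-rate mediation result depends on the overlap.

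**What to change.** Add to section 15.3: any mediation model with heart rate as outcome and a task-related brain mediator is fitted a second time, with the mediator re-extracted using the recorded cardiac and respiratory signals as first-level regressors. Both versions are reported. If the indirect effect appears only in the uncorrected version, support for Hypothesis 2 on heart rate is described as tentative. Keep the uncorrected values for the condition analyses and for cortisol mediation.

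How far this helps depends on how much contamination the regressors remove. At d = 0.8 and r = 0.3, removing half (assumed) lowers the bootstrap rate from 21.5% to 4.2%, and removing all of it gives 0%. In the task-locked check, adding the regressors cut false mediation to 0% and kept true mediation at 81%, in a setting where heart-rate fluctuations are not themselves neurally driven.

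The cost is one extra first-level run on signals already being collected, plus a few lines of text. The corrected version may also remove some true shared variance, so it should qualify the conclusion and not act as a veto.
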